5.1 AIM 1: TEMPORAL TRENDS

5.1.1. Overview of Design, Methods and Data Collection

Centers in SEARCH Phase 3 will continue to conduct population-based ascertainment of cases of diabetes in youth less than 20 years of age in the year of diagnosis for the period 2010 - 2014, using methods consistent with those employed in SEARCH Phase 1 and SEARCH Phase 2. This will involve identification, validation, confirmation of eligibility and uniqueness of cases, and registration of the case both locally with identifiers and centrally with the SEARCH 3 Coordinating Center (CoC) without identifiers. The 2010 - 2014 cases will have their medical records abstracted and will be asked to complete a brief survey. A sample of 2012 cases will be invited to an in-person research visit. Case registration will proceed without disruption in the transition from the end of SEARCH Phase 2 (September 29, 2010) until the full implementation of the SEARCH Phase 3 protocol. All data collection will be performed under standardized protocols by centrally trained and certified staff.

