In-Person Research Visit (IPV): The IPV or "registry visit" in SEARCH 3 is designed to collect data on relevant dimensions of diabetes type (presence of autoimmunity, genetic susceptibility to autoimmunity, insulin sensitivity, insulin secretion) and data informing the clinical presentation of diabetes. We will also store (by separate consent) blood, serum, plasma and urine for future genetic and non-genetic analyses. In keeping with the time-stratified sampling approach initiated in SEARCH 2, only the incident 2012 cohort will be eligible to participate in the registry visit. An additional sampling approach will be implemented in SEARCH 3, in order to reduce participant burden and maximize study resources, without compromising the statistical power to detect trends in clinical characteristics over time. To maximize the number of minority participants and youth with T2D, eligible cases for SEARCH 3 registry visit are all cases >10 years old, regardless of ethnicity/race, all minority cases, regardless of age, all cases not T1, regardless of race or age, and 50% of NHW T1 cases <10 years old. Since some sites are not able to obtain race at the time of the assignment of the PID, if race is not available, all participants will be invited to the IPV. We will seek a 70% completion of the IPV among eligible youth.

Table 5-1: Summary of SEARCH3 Registry Data Collection						
	Eligible Cohorts	Core Variables	Clinical Presentation			
MRA	2010-2014	Date of birth, date of diagnosis, sex, provider- determined diabetes type, race/ethnicity, residence in the year of diagnosis	Weight/height at diagnosis, DKA at diagnosis, insulin use, acanthosis nigricans, diabetes autoantibodies and c-peptide assessment			
IPS	2010-2014	Date of birth, date of diagnosis, sex, self-reported race/ethnicity, residence in the year of diagnosis; health insurance; usual diabetes care, education of parents; youth > 18 yrs.	Treatment history, secondary diabetes, symptoms at presentation, acute complications, medications, family history, contact information; reported height, weight			
IPV	2012		 Physical Exam: height, weight, waist circumference, BP, acanthosis nigricans Medication Inventory: list of currently prescribed medications Lab/specimens: diabetes autoantibodies (GAD65, IA2), HbA_{1c}, fasting glucose, C-peptide, lipids, urinary albumin/creatinine (spot sample) Repository: serum, plasma, DNA (by separate consent) and urine for storage on 1st morning void 			

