The content of the IPV for incident cases will be similar to SEARCH 1 and 2 (Table 5 - 1). However, unique to SEARCH 3, we will add a first morning void urine collection that the participant will bring to the clinic. Urinary albumin and creatinine will be measured to obtain an albumin/creatinine ratio on a spot urine sample. Samples will not be collected during the visit on participants who are pregnant or menstruating, have had a fever greater than 100 degrees in the past two hours, or who have taken an antibiotic in the past seven days for a urinary tract infection. A dipstick test will also be performed to test for the presence of blood or leukocytes by the central laboratory. Urine will also be stored (first morning void only) to assess other markers of nephropathy in the future. (8/11)

The following will be collected for the IPV incident cases: fasting blood and urine for laboratory measurements and storage, and a brief physical examination as outlined below.

• Blood measures: Diabetes autoantibodies (GAD65, IA-2); (ZNT8 will be added after the assay is standardized); HbA_{1c}, fasting glucose and C-peptide, lipids (total

cholesterol, HDL-Cholesterol, LDL-Cholesterol, triglycerides), HLA risk genotypes

- Urine measures (spot and first morning void): Urinary albumin and creatinine (from spot urine collection)
- Physical examination: Height, weight, blood pressure, assessment of acanthosis nigricans, waist circumference (NHANES and minimum waist methods) on participants who are 3 years of age or older at the time of the visit
- Medication inventory: List of currently prescribed medications.

SEARCH participants with an IPS will be invited to complete the IPV if they meet the following eligibility criteria. If <10 years of age and have type 1 diabetes, we will invite 50% of non-Hispanic White and 100% of all minority youth to participate in the IPV. All youth with type 2 diabetes will be invited to the visit. To encourage IPV participation, a remuneration of \$80.00 in cash or gift cards will be offered. Some centers may offer assistance with transportation in order to facilitate these visits. We will seek to complete a 70% rate among those participants invited to the IPV (Table 5-2).

Table 5-2. Estimated Number of Cases Registered, and Participating in the IPS and IPV								
Per Year								
Center	Estimated 2	N Incide	nt cases/year	Estimated N	Estimated N			
	NHW<10	Other	Total	IPS/year	IPV/year*			
SC	70	206	276	248	179			

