6.2. TEMPORAL CHANGES IN CLINICAL CHARACTERISTICS (Research Question 1.3)

Another research question focuses on assessing potential temporal changes in the demographic and clinical characteristics of youth with diabetes over time. Analysis of variance (for continuous measures like age and HbA_{1c}) and logistic regression (for dichotomous measures like prevalence of autoimmunity) will be used to assess changes in these outcomes over time. Time will initially be entered as a categorical variable to check for any differences over time. Time will then be considered continuously to check for consistent changes over time (slopes). Time by covariate interactions will be assessed to

determine if the slopes differ by level of important covariates (e.g., does the change in age over time differ for males and females). In Table 6.2, we show the slopes that can be detected with 80% power using the data through 2014, assuming that 1) onset age will be available each year and data for the other measures will be available for cohorts incident in 2002-2006, 2008, and 2012; 2) the sample sizes for onset age and for variables of interest among T2D youth will remain constant; and 3) the sample size for variables of interest among T1D youth will remain constant between 2002 and 2008 and will be 5/6(N) for 2012 (due to sampling only 50% of the NHW age <10 years). For example, there are about 970 incident T1D cases per year with an IPV in our surveillance area. The mean age of newly diagnosed T1D cases in 2002 was 9.4 years with a standard deviation of 4.7 years. Using data through 2014, we can detect a yearly change in onset age of 0.031 years (e.g., 9.4 in 2002 vs 9.0 in 2014). Approximately 84% of T1D had evidence of autoimmunity in 2002. With a sample size of approximately 440 for diabetes autoimmunity each year it is collected, we'll be able to detect a change of 0.6% per year (e.g., 84% in 2002 vs 90% in 2012).

Table 6.2 - Changes in Clinical Presentation, By Type, Detectable with 80% Power in 2014						
Variable	Mean (SD)	N per year	Detectable change			
T1D						
Onset Age (years)	9.4 (4.7)	970	0.031			
BMI-z	0.6 (1.0)	500	0.015			
HbA_{1c} (%)	7.9 (1.6)	470	0.025			
Insulin Sensitivity	10.3 (3.3)	430	0.054			
FCP (ng/ml)	0.5 (0.5)	470	0.008			
Autoimmunity (%)	84% (36%)	440	0.006			
DKA (%)	30% (46%)	760	0.006			
T2D						
Onset Age	14.3 (2.8)	250	0.037			
BMI_z	2.1 (0.7)	85	0.026			
HbA _{1c}	7.5 (2.4)	85	0.088			
Insulin Sensitivity	4.6 (2.8)	75	0.109			

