8.2. OVERVIEW: BACKGROUND INFORMATION

SEARCH Phase 3 will be conducted in two components, a Registry Study and a Cohort Study. Both components will be completed at all five SEARCH clinical centers, and the Coordinating Center and Central Laboratory will be the same for both components. No individual will be excluded on the basis of gender or race/ethnicity. Since the focus of this study is to learn more about the impact of diabetes on people who are less than 20 years of age at the time of diagnosis, this study includes children, adolescents, and young adults. This study does not involve fetuses, neonates, prisoners, or institutionalized individuals. Young women, who are pregnant and eligible for the study, will not be scheduled to participate in an in-person visit (IPV) until at least six weeks after the completion of the pregnancy.

The SEARCH Registry Study will involve ascertainment of cases diagnosed in the calendar years 2010 - 2014. Registered cases in all five incident years will be asked to complete an initial participant survey (IPS). The survey will be used to validate a diagnosis of diabetes, to confirm study eligibility, and to obtain essential core data elements. For the incident years 2011 and 2013, potentially eligible participants will be invited to participate in a baseline (IPV). Cases of secondary diabetes or any other specific types of diabetes, however, will be excluded from the study visit. Local study personnel will send study newsletters and conduct other local activities in order to try to maintain contact with these cases to allow for recruitment of these persons for future ancillary studies.

Based on previous SEARCH incidence data, we anticipate approximately 1,316 new cases of diabetes to occur per year in the base populations of these five centers. Therefore, we anticipate a total of approximately 6,000 new cases to be identified and registered for the

period throughout the grant period. This includes the 2010 cases that would be identified and registered starting September 30, 2010. We will attempt to have an IPS completion rate of 90% of all registered participants. We also anticipate approximately 1,700 participants will be involved in the IPV for the 2011 and 2013 incident years.

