8.7.5. In-Person Research Visit (IPV)

The IPV for of SEARCH 3 was designed to collect data on relevant dimensions of diabetes type (presence of autoimmunity, genetic susceptibility to autoimmunity, insulin sensitivity, insulin secretion) and data informing the clinical presentation of diabetes in youth. Only cohorts incident in 2011 and 2013 will be eligible to participate in the IPV. To maximize the number of minority participants and youth with T2D, cases that will be eligible to participate in the SEARCH 3 IPV are 100% of minority youth, regardless of age and type, 100% of youth age ≥ 10 years at diagnosis, regardless of race/ethnicity and type, and 50% of NHW youth age < 10 years who have type 1 diabetes. The content of the IPV will be similar to SEARCH 1 and 2 and will consist of collection of fasting blood and urine for laboratory measurements and storage and a physical examination.

- Measurements made to inform dimensions of diabetes type are DA (GAD65, IA-2 with the proposed addition of the novel ZnT8 antibody, once assays are standardized);
- Validated insulin sensitivity index (waist circumference, HbA_{1c}, triglycerides);
- Urinary albumin and creatinine;
- Standard lipid measures;
- HLA risk genotypes and fasting C-peptide (FCP) (plasma glucose will be measured in order to interpret FCP);
- The IPV physical examination, conducted on children over the age of 3 years, will consist of height, weight, systolic and diastolic blood pressure, waist circumference and a standardized examination to determine the presence or absence of acanthosis nigricans. Height will be measured in centimeters using a

stadiometer. Weight will be measured in kilograms using an electronic scale. Blood pressure will be measured using the aneroid sphygmomanometer. The NHANES and natural waist methods will used to measure waist circumference.

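### The registry in-person visit is limited to the 2012 cohort in Sections 5A and 6A but to the 2011 and 2013 cohorts in Section 8A, and the expected visit numbers need restating

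*Protocol*

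**What the plan says.** **Visit years, Sections 5A and 6A.** Protocol 5.1.1: "A sample of 2012 cases will be invited to an in-person research visit". Protocol 5.1.2: "only the incident 2012 cohort will be eligible to participate in the registry visit". Table 5-1 lists 2012 as the only eligible cohort in its IPV row. Section 6A, 6.2, builds Table 6.2 on the assumption that onset age is known every year and that "data for the other measures will be available for cohorts incident in 2002-2006, 2008, and 2012".

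**Visit years, Section 8A (registry human subjects).** Protocol 8.7.5: "Only cohorts incident in 2011 and 2013 will be eligible to participate in the IPV". Protocol 8.2 names the same two years and anticipates that "approximately 1,700 participants will be involved in the IPV for the 2011 and 2013 incident years". The same section gives the annual case load: "we anticipate approximately 1,316 new cases of diabetes to occur per year in the base populations of these five centers".

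**Sampling and expected numbers.** For type 1 cases under 10, 5.1.2 states that "we will invite 50% of non-Hispanic White and 100% of all minority youth to participate in the IPV". It also invites every case that is not type 1, and everyone where race is unknown when the participant ID is assigned. The completion target is 70%. Table 5-2 gives 343 NHW cases under 10, 930 others, 1,273 in total, and 820 visits per year.

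**The concern.** Sections 5.1.2 and 8.7.5 each claim exclusivity for their own years, so no reading satisfies both. A 2012 case invited under 5.1.2 is ineligible under 8.7.5, and the reverse holds for 2011 and 2013 cases. This is current text in both places, not an amendment history.

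The years also set the time points and the number of observations for the characteristics measured only at the visit (HbA1c, C-peptide, insulin sensitivity score, study-measured autoantibodies) in Research Question 1.3. The power table and the visit forecast in the human-subjects section appear to rest on different designs. Separately, the annual forecast in Table 5-2 looks too high for the sampling fraction given beside it.

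**Working it through.** **1. Which years lie behind Table 6.2?**
Detectable slope = (z₀.₉₇₅ + z₀.₈₀) × SD / √(Σ nᵢ(tᵢ − t̄)²), with 1.960 + 0.842 = 2.802. Power of 80% is stated for the table; two-sided alpha of 0.05 is assumed, as stated for Table 6.1. SDs and yearly n come from Table 6.2.

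Type 2, equal n per year, t counted from 2002:
- 2012 only (t = 0, 1, 2, 3, 4, 6, 10): Sxx = 166 − 26²/7 = 69.4
- 2011 and 2013 (t = 0, 1, 2, 3, 4, 6, 9, 11): Sxx = 268 − 36²/8 = 106.0

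| Type 2 measure | SD, n/year | Stated | 2012 only | 2011 + 2013 |
|---|---|---|---|---|
| BMI-z | 0.7, 85 | 0.026 | 0.0255 | 0.0207 |
| HbA1c | 2.4, 85 | 0.088 | 0.0875 | 0.0708 |
| Insulin sensitivity | 2.8, 75 | 0.109 | 0.1087 | 0.0880 |
| Fasting C-peptide | 1.9, 85 | 0.069 | 0.0693 | 0.0561 |

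The stated values follow from a single 2012 visit year. The ratio of the two designs is √(69.4/106.0) = 0.81, so slopes would be about 19% smaller with 2011 and 2013.

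Type 1, with the stated 5/6 weight on the new cohort(s): Sxx = 62.7 (2012) against 95.1 (2011 and 2013); ratio √(62.7/95.1) = 0.81, again about 19%. BMI-z, HbA1c and insulin sensitivity compute to 0.0158, 0.0261 and 0.0563 for 2012, and to 0.0128, 0.0212 and 0.0457 for 2011 and 2013, against stated 0.015, 0.025 and 0.054. The 2012 design is much the closer. With full n in 2012 (Sxx 69.4) these three rows agree to rounding; for example HbA1c is 2.802 × 1.6/√(470 × 69.4) = 0.025. The 5/6 weight may therefore not have been applied, but the visit year is 2012 either way.

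**2. Where does 1,700 come from?**
Scale the Table 5-2 yield to the Section 8A case count and take two cohorts: 2 × 1,316 × 820/1,273 = 1,695. So 1,700 is a two-cohort total and 820 is a one-year figure. They agree once this is allowed for.

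**3. Does 820 follow from the stated sampling?**
Visits = 0.70 × (f × NHW under 10 + Other), where f is the fraction of NHW under 10 invited.

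| Center | NHW <10 | Other | Stated | f = 0.50 | f = 0.70 |
|---|---|---|---|---|---|
| SC | 70 | 206 | 179 | 168.7 | 178.5 |
| OH | 51 | 113 | 104 | 96.9 | 104.1 |
| CO | 132 | 244 | 236 | 217.0 | 235.5 |
| CA | 15 | 213 | 156 | 154.3 | 156.4 |
| WA | 75 | 154 | 145 | 134.0 | 144.5 |
| Total | 343 | 930 | 820 | 771.0 | 819.1 |

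At f = 0.50 the total is 0.70 × (171.5 + 930) = 771, which is 49 visits (6%) below 820. At f = 0.70 every center is within one visit of its stated figure. Two other rules come near the total but miss California (stated 156): 75% completion with 50% sampling gives 826 in total and 165 there; 90% × 70% with no sampling gives 802 and 144.

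Section 6.2 attributes its 5/6 factor to 50% sampling. Treating all 343 as type 1 among 970 type 1 cases, 50% sampling retains 1 − 0.5 × 343/970 = 0.82, near 5/6 = 0.83; 70% would retain 1 − 0.3 × 343/970 = 0.89. Section 6A therefore fits 50%, and Table 5-2 does not.

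**The case against.** The year conflict has no good defense. The fair objections concern what may be built on it.

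- **771 is not an exact replacement.** The Table 5-2 column holds all NHW cases under 10, and 5.1.2 invites every non-type 1 case and every race-unknown case, so the effective fraction exceeds 50% by an amount the protocol does not give. This stands: 771 is a floor, and the center figures at 50% should not be printed as corrections. It does not rescue 820, however. Reaching 70% needs 0.5(1 − x) + x = 0.7, so x = 0.40 of NHW cases under 10 in those two groups. No figure supports that; the Executive Summary says type 1 is the majority at ages 0–9 in all groups, and 5.1.2 says only some sites lack race.
- **The asterisk on the visit column has no note in the text available.** It may state the basis of the column. That is a reason to ask, not to assert an error with certainty.
- **70% is a back-fit.** The match is close but not exact: Colorado computes to 235.48 against 236, and the total to 819 against 820.
- **A reader might lower the figure by a further 10%** because 5.1.2 ties the invitation to a completed initial participant survey with a 90% target. The same section allows that survey at the start of the visit, so the protocol does not support the reduction.
- **A reader might infer that every Research Question 1.3 trend is affected.** It is not. Onset age is available each year, and Table 5-1 has DKA and height and weight at diagnosis abstracted from records for all 2010–2014 cases.
- **A reader might infer that the study is underpowered.** Under 2011 and 2013 Table 6.2 would be conservative, and it takes no input from Table 5-2.

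**Conclusion.** The point holds for the visit years: 5.1.1, 5.1.2, Table 5-1 and 6.2 describe one visit cohort (2012), while 8.2 and 8.7.5 describe two others (2011 and 2013). Table 6.2 is valid as computed only for the first design; the second would give detectable slopes about 19% smaller for the visit-based measures, assuming two-sided alpha of 0.05 and the per-year n of Table 6.2. The gap between 1,700 and 820 is this same one-versus-two-cohort conflict, combined with different annual case counts (1,316 and 1,273); it is not a further error.

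The Table 5-2 discrepancy is secondary. The stated 50% sampling and 70% completion give about 771 as a floor, up to 6% below 820, and no power statement depends on it. What individual review boards approved cannot be judged from the protocol, because consent materials are customized locally.

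**What to change.** 1. State one set of visit years in 5.1.2, 6.2, 8.2 and 8.7.5, and carry it through 5.1.1 and Table 5-1.
2. If 2012 only: replace the 1,700 in 8.2 with the one-cohort figure. If 2011 and 2013: recompute the visit-based rows of Table 6.2.
3. Recompute the visit column of Table 5-2 from the stated 50% sampling and 70% completion, with an explicit allowance for non-type 1 and race-unknown cases, or state the basis for 820.
4. Use one annual case count, 1,273 or 1,316, in Table 5-2 and 8.2.

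The cost is protocol wording, a short recalculation and a notification to the review boards. The forecast number of visits may fall slightly.

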5.1.3. Mortality Surveillance

To address Aim 3 of this study, we will conduct surveillance of mortality including allcause and cause-specific mortality in the incident cohorts. All centers will systematically identify deaths that occur between the date of diagnosis and December 31, 2010 among youth in the 2002-2008 incident cohorts (registered during SEARCH 1 and 2) using the National Death Index (NDI) as the primary source, plus individual case reports of deaths made to the study team during the course of the study. The NDI is a central computerized index of death record information from State vital statistics offices nationwide. By the spring 2012, the NDI will include death record information through 2010. Due to HIPAA and IRB considerations that preclude this activity from being done centrally, each center will submit their cases to the NDI. The NDI Plus service will be used so that any potential matches are returned with the cause of death codes. Subjects who are known to be deceased will be submitted separately to obtain cause of death. Records will be searched for all years for which vital status cannot be confirmed. Death certificates and reports of deaths by immediate family members or the participant's health care provider will also be considered definitive evidence of mortality. Next of kin will not be contacted when a death is identified.

Based on the 9,448 incident 2002-2008 cases registered to date, we anticipate that we will have $\approx 46,863$ person-years (p-y) of follow-up with a mean follow-up time of 5 years for the cohort (35,836 p-y for T1D; 9.144 p-y for T2D). P-Y of follow-up will be calculated from the date of diagnosis until the date of death or December 31, 2010. We will examine all-cause mortality as well as cause-specific mortality. Cause of death will be obtained from the codes on the death using a standardized international protocol. In the analyses of risk and cause of death using this population-based cohort, we will evaluate the association between mortality and cause-specific mortality by gender, age, race/ethnicity, and DM type. In addition, targeted exploratory subgroup analysis will be conducted to examine the associations between variables measured at SEARCH visits including history of acute complications.

SEARCH Phase 3 Protocol - Section 5B Cohort Study Data Collection Table of Contents

5.	DATA	COLLECTION 1
5	5.1. SE	EARCH COHORT STUDY VISIT METHODS 1
	5.1.1.	Eligibility and Anticipated Sample Size 1

5.1. SEARCH COHORT STUDY VISIT METHODS

5.1.1. Eligibility and Anticipated Sample Size

Individuals registered in the SEARCH cohort with a diagnosis of non-gestational diabetes in incident years 2002-2005, 2006 and 2008 and who completed a SEARCH baseline inperson visit in one of the SEARCH clinical centers will be eligible for the new SEARCH Cohort Study once they have had diabetes for at least 5 years. We will determine an algorithm that optimizes duration of disease over the data collection years of the Cohort Study, considering both diagnosis year and the timing of the most recent SEARCH visit during the SEARCH 2 protocol. We anticipate that the average duration of diabetes will be 8-9 years (range 6-14 yrs diabetes duration), and the average age of participants at the time of the SEARCH Cohort Visit will be about 20 years (range 8-32 yrs old). Our goal is to have 80% of eligible members of the cohort attend the proposed SEARCH Cohort Study visit, for a total of 3145 participants with a Cohort Study visit.

Of the 20% not attending the research clinic visit, an additional 10% will be participate by completion of surveys by telephone or internet, for a total of 90% inclusion or 3550 individuals. Based on proportions of youth in sub-groups of diabetes type and race/ethnicity, the anticipated numbers and characteristics of anticipated participants in the SEARCH Cohort Study data collection are displayed in Table 5-1.

Table 5-1. Anticipated Sample Size and Characteristics: SEARCH Cohort Study (2002 - 2006, 2008)												
	S	SC	0	Н	CO	C	C.	A	W	/A	All	
Туре	80%	90%	80%	90%	80%	90%	80%	90%	80%	90%	80%	90%
Race/Ethnicity												
Type 1												
NHW	405	456	386	434	711	800	98	110	410	461	2010	2261
Other	175	197	58	65	188	211	185	209	94	106	700	788
Type 2												
NHW	38	42	30	34	16	17	7	8	16	18	107	119
Other	106	120	42	47	79	95	83	97	18	23	328	382
ALL	724	815	516	580	994	1123	373	424	538	608	3145	3550

